9.3.2.2 Radiographic Clinical Responses

For each treatment arm, for patients with objective disease, using immune-related response criteria (irRC) criteria, the proportion of patients achieving a complete or partial response will be determined and reported with 95% confidence intervals.

9.3.2.3 Modulation of Effector and Regulatory T Cells

The secondary outcome measures of T cell immune activation will be compared between the two treatment arms. Exploratory analyses of antigen-specific T cell responses to PAP and PA2024 will be measured at weeks 0, 4(study day 1), 7(day 22), 10(day 43), 13 (day 64), 16 (day 85), 20 (day 113), 32 (day 197) with IFNg ELISPOT. Samples will be obtained just prior to treatment. A T cell response to each of the antigens will be defined as ≥ 10 spots/300,000. For each antigen (PAP and PA2024), the proportion of positive responses by treatment arm at week 20 will be calculated and presented with 95% confidence intervals. Agreement in antibody and T cell responses will be explored at each time point with McNemar's test for paired binary data. In addition, a test of when a T cell immune response is first recognized will also be identified using ANOVA methods when the T cell response is evaluated as a continuous variable. There will not be any adjustment for multiple comparisons for these exploratory analyses.

Exploratory ANOVA analyses for mixed models will also be used to compare the magnitude or the change from baseline in activated CD4 and CD8 T cells to week 7, 10, 13, 16, and 20 of treatment between the two treatment arms. Activation markers to be assessed on CD4 and CD8 T cells by flow cytometry will include ICOS/ICOS-L; OX40/OX40-L; 41BB/41BB-L; PD-1/PD-L1 and PD-L2; CD69, and HLA-DR. Similar comparisons of the magnitude or change from baseline in FoxP3+ CD4+ Regulatory T cells at these same time points will be evaluated.

Additional exploratory analyses again using ANOVA methods will be performed to determine whether there is a difference in baseline levels or change by week 14 and 20 in T cell activation markers between those achieving a PSA decline of at least 30% or not.

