3.2 Phase 2 Design

Once the ipilimumab dose is established for each study arm, the randomization between the immediate and delayed arms will resume accruing a total of 27 evaluable randomized patients per study arm.

Randomized patients treated in the phase I at the same dose used in the Phase 2 study will be included for immune response analysis; thus patients accrued in the randomized component of the Phase I trial can be included for analysis of the study objectives.

Once written informed consent is obtained and the patient has undergone screening and determined to be eligible for the trial, treatment with SipT will begin. The patient will be randomly assigned following the second dose of SipT to one of the two treatment groups in a 1:1 ratio using a block design to maintain a balance in treatment assignment. Randomization will be stratified by site (UCSF and MD Anderson). The randomization will be performed by the study statistician at UCSF. At the time of randomization, a unique patient study identification number will be assigned to each patient. This study identification number must be included on all submitted forms and specimens.

Patients will receive induction treatment with 4 doses of ipilimumab on a 21-day cycle. As durable disease stabilization and/or objective tumor response can be seen after early progression, it is recommended that, in the absence of dose-limiting toxicities, all four doses of ipilimumab be administered over the initial 12 weeks even in the setting of apparent clinical progression, providing the subject's performance status remains stable.

All subjects who enter the induction period, including those who may have discontinued treatment for drug-related AEs and/or who have evidence of clinical progression during the induction period, should obtain a 12-week tumor assessment.

Clinical progression warranting alternative anti-cancer treatment should be considered only in subjects whose overall tumor burden appears to be substantially increased and/or in subjects whose performance status is decreased.

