9 STATISTICAL METHODOLOGY

9.1 Sample Size Considerations

9.1.1 Safety Lead-in

Six patients at the 3 mg/kg dose of ipilimumab will be randomized to Arm 1 and 2, immediate versus delayed ipilimumab after 4 doses of SipT. If DLTs are encountered as defined above (Section 3.1), then one or both arms may be discontinued. 6 patients will be required to complete this phase of the study.

9.1.2 Phase 2

Primary Immune Objective: This is a multicenter non-comparative randomized Phase 2 trial with the primary objective of immunologic efficacy in addition to safety. Immune response is defined as an IgG antibody response to either PAP or PA2024 by study week 20. The IgG antibody response will be determined with an ELISA assay with a positive response defined as titer > 1:400. To achieve a 40% immune response rate indicating immune activity versus a null hypothesis of 15% indicating lack of immune activity assuming a 2-sided type I error of 5% and 81% power will require 27 total patients per arm. This is based upon the exact binomial test for a single sample. The null hypothesis of 15% is based off an observed anti-PAP IgG response rate of 17.7% seen at a similar time interval in patients treated with sipuleucel-T in the three phase 3 clinical trials⁴⁶. Therefore, an additional 21 patients beyond the safety lead-in phase will be accrued to each arm (an additional 42 patients). The total number of evaluable patients for the Phase 2 study will be 54 patients with accrual up to 66 patients possible. Patients will be accrued at UCSF and MDACC with the randomization to ipilimumab timing stratified by institution.

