Secondary Immune Objectives: The sample size with 27 patients in each arm is sufficient to detect a mean difference between the two study arms in immune modulation, a secondary objective, for an effect size (standardized unit) of at least 0.69 for normally distributed variables. Similarly, the sample size is sufficient to detect at least a 37% difference between the two treatment groups in proportions of patients displaying a specific outcome using Fisher's exact test (e.g. 33% versus 70% achieving a certain change in an immune parameter). For both types of tests a level of significance of 0.05 for a directional test and power of at least 0.80 is assumed. Directional tests will be performed to test for an effect due to the timing of ipilimumab. A directional test is being used because a greater immune effect is expected with immediate administration of ipilimumab.

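### Randomization is stratified by site, but the planned between-arm immune comparisons leave site out; the exploratory PSA-responder analysis names no arm term and refers to a week 14 that is not sampled

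*Combined protocol and SAP*

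**What the plan says.** **Design.** Section 3.2 allocates patients "in a 1:1 ratio using a block design to maintain a balance in treatment assignment" and names site (the two centres) as the stratification factor. Section 9.1.2 repeats this: "with the randomization to ipilimumab timing stratified by institution".

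**Power for the secondary immune comparison.** Under its secondary immune objectives, 9.1.2 states: "The sample size with 27 patients in each arm is sufficient to detect a mean difference between the two study arms in immune modulation", for an "effect size (standardized unit) of at least 0.69 for normally distributed variables". For binary outcomes it refers to Fisher's exact test and gives the example "33% versus 70% achieving a certain change in an immune parameter". Both statements assume a directional 0.05 level and power of at least 0.80.

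**Analysis.** Section 9.3.2.3 opens with "The secondary outcome measures of T cell immune activation will be compared between the two treatment arms". It plans mixed-model ANOVA of activated CD4 and CD8 T cells, and similar comparisons of FoxP3+ regulatory T cells, between arms at weeks 7, 10, 13, 16 and 20. Site is not mentioned. The one stratified method in the plan, the Mantel-Haenszel statistic in 9.3.1.2, is stratified by arm.

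**Responder analysis.** The last paragraph of 9.3.2.3 uses ANOVA to look at marker levels at baseline, and at "change by week 14 and 20 in T cell activation markers between those achieving a PSA decline of at least 30% or not". No arm term is named. The same section lists T cell samples at weeks 0, 4, 7, 10, 13, 16, 20 and 32.

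**The concern.** An analysis should normally reflect the factors that restricted the randomization. Balancing arms within site makes the arm difference more precise if sites differ. A test that ignores site leaves the between-site variation in its error term, so it overstates the standard error and gives that precision away. The comparison at stake serves a stated secondary objective (2.2) and has its own power statement.

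The responder analysis raises a different issue. Grouping patients by PSA decline alone means that, if both PSA response and marker level differ by arm, the arm difference can appear as an association between marker and response.

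Finally, an analysis tied to a week with no scheduled sample cannot be run as written. Someone would have to choose a substitute week, possibly after seeing the data.

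**Working it through.** **1. The plan's own figures.** The inputs from 9.1.2 are 27 per arm, 0.69 SD and one-sided 0.05. The noncentrality is 0.69 × √(27/2) = 2.535. The noncentral t distribution with 52 df gives power 0.804. Exact enumeration of the one-sided Fisher test at 33% versus 70% gives 0.802. Both agree with the stated power of at least 0.80 and neither is disputed.

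**2. Leaving site out.** Assumptions: two sites of about equal size, arms balanced within site, and a site difference of g within-site SD. The documents give no value for g. The unadjusted error variance is inflated from 1 to about 1 + g²/4, so the standard error is too large by k = √(1 + g²/4). Then:

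- true size ≈ 1 − Φ(1.645 k)
- power at 0.69 within-site SD ≈ Φ(2.535 − 1.675 k), where 1.675 is the one-sided 5% t value on 52 df

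| g | k | true size, no site | power, no site | power, site in model (simulated) |
|---|---|---|---|---|
| 0 | 1.000 | 5.0% | 81% | 80–81% |
| 0.5 | 1.031 | 4.5% | 79% | 80% |
| 0.8 | 1.077 | 3.8% | 77% | 80% |
| 1.0 | 1.118 | 3.3% | 75% | 81% |

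Simulation (60,000 trials, 14/13 by site in each arm) agrees. Without site, the size is 4.5, 4.0 and 3.3% and the power 79, 77 and 74% for g = 0.5, 0.8 and 1.0. With site, the size stays at about 5%. With a 25/75 site split, g = 1.0 gives power 76% without site and 81% with it (8,000 runs).

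The scale matters. If 0.69 is read in total SD while g stays in within-site SD, power is 81, 82 and 83% without site and 83, 85 and 88% with it. The gain is of similar size, but two units are mixed. The table keeps to one.

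**3. Responder analysis.** Suppose there is no link between marker and response within either arm, and the arms differ by d in the marker. The apparent responder difference is then d × (share of responders in Arm 1 − share of non-responders in Arm 1). The response rates below are assumed, with equal arms and d = 0.69.

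- 30% versus 10% response: 0.30/0.40 = 75.0% of responders and 0.70/1.60 = 43.75% of non-responders are in the first arm. The spurious difference is 0.69 × 0.3125 = 0.22 SD, and the simulated two-sided false-positive rate is 9.4%.
- 40% versus 10%: 0.40/0.50 = 80% and 0.60/1.50 = 40%. The spurious difference is 0.69 × 0.40 = 0.28 SD, and the false-positive rate is 12.4%.
- 20% versus 20%: no spurious difference; the rate is 4.8%.

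With arm in the model the rate is between 4.6 and 5.5% in these cases.

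**4. Week 14.** Every week-day pair in 9.3.2.3 satisfies week = 4 + (day − 1)/7: Day 64 is week 13, Day 85 is week 16 and Day 113 is week 20. Week 14 is therefore Day 71. The calendar windows of ±3 days (6.1) cover Days 61–67 and 82–88. Counting 14 weeks from Day 1 instead gives Day 99, which is not a listed sampling day either.

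**The case against.** The case for leaving the plan alone is substantial, and much of it stands.

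- **No error in inference.** A reader might infer that omitting site biases the arm comparison or produces false positives. It does neither: the estimate stays unbiased and the test errs on the conservative side.
- **No documented site effect.** Blood from all patients for the ELISA and ELISPOT assays goes to one laboratory (6.1, footnote d), which removes between-laboratory variation. Differences in transit or patient mix are possible but are not shown. Where change from baseline is analysed, a constant additive site shift cancels.
- **Status of the analyses.** The trial is declared non-comparative. The mixed-model and responder analyses are labelled exploratory. Fisher's test appears only in the sample-size text, and 9.3.1.2 states no between-arm model, so there is nothing there to adjust.
- **Pooling is inferred.** Section 9.3.2.3 says only that ANOVA methods will be used and lists no terms. An analyst could include arm. The plan simply does not commit to it.
- **Dose exposure.** A reader might argue that the arms always differ by one ipilimumab dose. On the calendar, with samples taken before dosing, Arm 1 has had 3 planned doses and Arm 2 has had 2 at week 13, and 4 versus 3 at week 16. At baseline neither arm has had any, and by week 20 both have had four. The argument therefore does not cover two of the three time points in the responder analysis.

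These points limit the severity. They do not remove the mismatch between randomization and analysis, nor the unsampled week.

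**Conclusion.** The point holds as a low-severity improvement. Site is a randomization factor that the between-arm immune comparisons ignore. The loss is about 1 to 2 power points at a site difference of 0.5 within-site SD and about 5 to 6 points at 1.0. Those figures rest on an assumed site effect and roughly equal sites. With no site effect, nothing material is gained or lost.

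The responder analysis is at risk only if PSA response and marker level both differ by arm. The response rates used to illustrate that are assumptions.

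Week 14 is a plain inconsistency with the sampling schedule. A reader might take it as a slip for week 13. Week 16, or the last sample up to week 14, is also possible, and the documents do not settle which was meant.

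The primary one-sample exact test in each arm, and the 27 per arm that it supports, are untouched.

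**What to change.** - Name site as a factor in the between-arm immune models of 9.3.2.3. Wherever a between-arm comparison of a binary immune outcome is made, use an exact test stratified by site.
- Include arm and site in the PSA-responder ANOVA.
- Reconcile week 14 with the sampling list by naming, before analysis, the sampled week intended.

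The cost is wording in the analysis section and one degree of freedom per added term. Sample size, visits and assays do not change.

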9.3 Methods for Analysis

9.3.1 Primary Endpoints

9.3.1.1 *Safety Lead-in: Assess the safety of combining ipilimumab with SipT.*

Toxicities will be reported for each study arm at each dose of ipilimumab administered with descriptive statistics (e.g. proportions) by tabulating the frequency of the maximum grade occurring for each patient for each type using NCI CTC v. 4.0 criteria. As described above the type and grade of all such IraEs will be tabulated by treatment arm. Toxicity results will be presented indicating occurrences during the first 20 weeks of protocol therapy and those occurring later.

9.3.1.2 *Phase 2: Determine whether the timing of ipilimumab administration impacts PAP and PA2024 specific immune responses by SipT*

The primary immune study hypothesis to assess the frequency of observing an immune response to PAP and/or PA2024 by week 20, when the induction ipilimumab therapy is completed, for each of the two ipilimumab schedules will be tested using the single sample binomial exact test. The IgM and IgG antibody responses to PAP and PA2024 will be assessed with an ELISA assay at baseline and week 20 after the start of sipT treatment (day 113 of study treatment). A positive response will be defined as a titer > 1:400. The primary hypothesis will be tested by comparing the proportion of patients achieving an IgG immune response to PAP or PA2024 to the null hypothesis of 15% (based off an observed anti-PAP IgG response rate of 17.7% seen at a similar time interval in patients treated with sipuleucel-T in the three phase 3 clinical trials⁴⁶. using a single sample exact test for binary variables as defined above in the sample size justification. The same single sample test will be performed for IgM antibodies. The positive immune proportion for both IgG and IgM antibodies to PAP and to PA2024 with 95% confidence intervals will be used to summarize the results for each study arm. No adjustment for multiple comparisons will be made.

Exploratory analyses investigating the change in antibody response from baseline to week 20 when response is considered as a binary variable (positive or negative) will be investigated using the Mantel-Haenszel chi square statistic stratified by treatment arm. When the ELISA results are treated as continuous variables the change in each immune response will be analyzed using analysis of variance (ANOVA) methods.

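### Two exploratory immune analyses use tests that do not match their stated questions: McNemar's test for antibody/T-cell agreement, and an arm-stratified Mantel-Haenszel test with no defined table for antibody change

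*Combined protocol and SAP*

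**What the plan says.** **Agreement (section 9.3.2.3).** "Agreement in antibody and T cell responses will be explored at each time point with" McNemar's "test for paired binary data". No kappa, percent agreement or other concordance measure is named anywhere in the document. For the T-cell assay alone, "the proportion of positive responses by treatment arm at week 20 will be calculated and presented with 95% confidence intervals". The section also states: "There will not be any adjustment for multiple comparisons for these exploratory analyses".

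**Antibody change (section 9.3.1.2).** "Exploratory analyses investigating the change in antibody response from baseline to week 20 when response is considered as a binary variable" "will be investigated using the Mantel-Haenszel chi square statistic stratified by treatment arm". The rows and columns of the table are not given. The next sentence plans an ANOVA of change when the ELISA result is treated as continuous. The section also summarises each arm by "The positive immune proportion for both IgG and IgM antibodies to PAP and to PA2024 with 95% confidence intervals".

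**Timing.** Antibody responses "will be assessed with an ELISA assay at baseline and week 20 after the start of sipT treatment"; section 7.1.1 likewise names only baseline and week 20. The ELISPOT schedule in section 9.3.2.3 has eight times, from week 0 to week 32.

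**The concern.** Agreement is a property of the joint distribution: do the same patients respond on both assays? McNemar's test discards the concordant patients and compares the margins. The same p-value can therefore come from good agreement or from none. A non-significant result could be read as concordance when the assays are unrelated, and a significant one as discordance when most patients agree. The planned positive proportions are also margins, so they cannot fill the gap.

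For antibody change, baseline and week-20 readings come from the same patients, but the only stratum named is the arm. Depending on the layout, the test either uses a variance that is wrong for paired data or answers a different question. Seroconversion could be missed when a patient's two results are positively correlated. What is at stake is how the exploratory immune results are read, not the primary conclusion.

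**Working it through.** **Inputs.** From section 9.1.2: 27 patients per arm, null rate 15%, target rate 40%, two-sided 5%, stated power 81%. The documents give no paired counts, baseline positivity or within-patient correlation, so all counts and rates from step 1 on are illustrative.

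**Plan's own figure.** Exact binomial, n = 27. Rejecting at 9 or more responders gives an upper tail of 0.0138 under 15% and power 0.816 under 40%. At 8 or more the upper tail is 0.0398, above 0.025. The stated 81% is reproduced. The plan states no figure for the two tests discussed here.

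**Step 1: McNemar against agreement.** Cells are a (both positive), b and c (discordant), d (both negative).

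- Exact McNemar: p = min(1, 2 x P[Bin(b+c, 1/2) <= min(b,c)]).
- Kappa = (po - pe)/(1 - pe). With both assays positive in 11/27, pe = (11² + 16²)/27² = 377/729 = 0.517.
- Cells 9, 2, 2, 14: po = 23/27 = 0.852, so kappa = (0.852 - 0.517)/0.483 = 0.69.
- Cells 4, 7, 7, 9: po = 13/27 = 0.481, so kappa = (0.481 - 0.517)/0.483 = -0.07.

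| a, b, c, d | Raw agreement | Kappa (95% CI) | McNemar p |
|---|---|---|---|
| 11, 0, 0, 16 | 100% | 1.00 | 1.0 |
| 9, 2, 2, 14 | 85% | 0.69 (0.42 to 0.97) | 1.0 |
| 4, 7, 7, 9 | 48% | -0.07 (-0.45 to 0.30) | 1.0 |
| 0, 11, 11, 5 | 19% | -0.69 | 1.0 |
| 11, 0, 6, 10 | 78% | 0.58 | 0.031 |

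Positive agreement, 2a/(2a+b+c), is 18/22 = 82% in the second row and 8/22 = 36% in the third. By enumeration, two unrelated assays each 40% positive give a non-significant result 97% of the time. Nested assays at 30% and 60% positive (70% agreement, kappa 0.44) give a significant one 86% of the time.

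**Step 2: antibody change, visit-by-response table within arm.** Suppose each arm goes from 4/27 to 8/27 positive. Per arm there are 54 readings, 12 of them positive. Week-20 positives are 8 observed and 6 expected, with variance 27 x 27 x 12 x 42/(54² x 53) = 2.377. Over two arms, chi-square = 4²/4.755 = 3.37, p = 0.067. Only margins enter, so the result is the same however readings pair within patients.

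With the patient as stratum, chi-square = (B - C)²/(B + C), where B and C are conversions and reversions pooled over arms:

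| Reversions per arm | B vs C | Chi-square | p | Pooled exact p |
|---|---|---|---|---|
| 0 | 8 vs 0 | 8.00 | 0.0047 | 0.0078 |
| 1 | 10 vs 2 | 5.33 | 0.021 | 0.039 |
| 2 | 12 vs 4 | 4.00 | 0.046 | 0.077 |
| 3 | 14 vs 6 | 3.20 | 0.074 | 0.115 |

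**Step 3: the other layout, baseline by week-20 status within arm.** Take 4 positive at both visits, 4 gained, 4 lost and 15 negative at both: zero net change. Observed minus expected is 4 - 64/27 = 1.630 per arm, and the summed variance is 2.438. Chi-square = 3.259²/2.438 = 4.36, p = 0.037. If no patient changes (10, 0, 0, 17 per arm), p < 0.001. This layout tests association, not change.

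**Step 4: operating characteristics of the step 2 layout.** Power is for an assumed 15% to 30%; false positives are with 20% at both visits. All tests combine both arms (54 patients) except the last power row.

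| Within-patient correlation | 0 | 0.3 | 0.5 |
|---|---|---|---|
| Power, arm as stratum | 0.47 | 0.46 | 0.45 |
| Power, patient as stratum | 0.47 | 0.59 | 0.75 |
| Power, pooled mid-p | 0.45 | 0.59 | 0.75 |
| Power, pooled exact | 0.37 | 0.50 | 0.65 |
| Power, exact within one arm (27) | 0.16 | 0.19 | 0.21 |
| False positives, arm as stratum | 0.051 | 0.020 | 0.006 |
| False positives, patient as stratum | 0.050 | 0.044 | 0.044 |

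At correlation -0.15 the arm-stratified test has 0.067 false positives and power about 0.48; the patient-stratified test has 0.052 and 0.42.

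**The case against.** The strongest reply is that both analyses are exploratory, that McNemar's test is valid for paired binary data, and that the 2x2 table it needs already contains the agreement counts. Kappa could be added later from planned data. All of this is true, and it keeps the point small. It does not make McNemar's test a measure of agreement: it is valid for comparing rates and should be labelled so.

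On antibody change, a reader might infer that the planned test simply ignores pairing. The document does not support that. The table is undefined, and a baseline-by-week-20 table keeps the pairing, though it answers a different question. What stands is that neither natural layout is a valid paired test of change.

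A reader might also infer that a paired test always does better. It does not. At zero correlation power is about 0.47 either way, and the pooled exact test falls to 0.37. With two reversions per arm in the illustration, the pooled exact p is 0.077 against 0.067 for the arm-stratified test. Exact tests within each arm have only about 0.16 to 0.21 power.

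Finally, the continuous ANOVA means the binary test is not the only planned look at antibody change.

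**Conclusion.** Minor. The agreement analysis is wrong as written, and that conclusion depends on no assumed rate: McNemar's test compares margins, and p = 1.0 is compatible with kappa anywhere from 1.00 to -0.69 in the tables shown.

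The antibody-change analysis is a smaller point. Its table must be defined, and arm as the only stratum does not give a valid paired test of change under either natural layout. In the visit-by-response layout the test is conservative if a patient's two readings are positively correlated, about right if uncorrelated, and above 5% false positives if negatively correlated. The size of any power gain rests on the assumed 15% to 30% rise and on a correlation that the documents do not give.

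A reader might infer that the trial's main immune result is in doubt. It is not: the primary test is a single-sample exact binomial test in each arm, and neither analysis enters it or the sample size.

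**What to change.** **Agreement.** At each visit where both assays are run, report the 2x2 counts, positive and negative percent agreement, and Cohen's kappa with a 95% CI. Keep McNemar's test only if labelled as a comparison of positivity rates. State which visits have ELISA results: sections 7.1.1 and 9.3.1.2 name baseline and week 20 only, while footnote d of the study calendar says the serial blood samples serve both ELISA and ELISPOT.

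**Antibody change.** Define the table. For one combined test, keep Mantel-Haenszel but make the patient the stratum; this equals McNemar's test on discordant pairs pooled over arms, and a mid-p version is an alternative. Per arm, tabulate conversions and reversions and give a 95% CI for the paired change, as estimates and not as separate tests.

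**Cost.** SAP wording and a few lines of code; no new data. Kappa is imprecise at n = 27 (0.69 has a 95% CI of 0.42 to 0.97) and uninformative if an assay has almost no positives, so the counts must accompany it. The patient-stratified test gains no power at zero correlation and loses some at negative correlation (0.42 against 0.48 at -0.15), where the arm-stratified test does not hold its 5% level.

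### Section 9.3.2.3 dates the first T cell response with ANOVA on mean ELISPOT values, which does not estimate onset, and states no contrast or decision rule (minor, exploratory)

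*Combined protocol and SAP*

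**What the plan says.** Section 9.3.2.3 plans IFNg ELISPOT against two antigens, PAP and PA2024, at week 0 and at seven later visits (weeks 4, 7, 10, 13, 16, 20 and 32). It defines a per-patient responder: "A T cell response to each of the antigens will be defined as ≥ 10 spots/300,000". It plans the proportion positive at week 20 by arm with 95% confidence intervals. It then adds that "a test of when a T cell immune response is first recognized will also be identified using ANOVA methods", and limits this to the case "when the T cell response is evaluated as a continuous variable". The section also states: "There will not be any adjustment for multiple comparisons for these exploratory analyses".

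For the onset analysis the section does not say whether each visit is compared with baseline or the arms with each other. Nor does it say whether an overall test comes first, whether the model allows for repeated measures, whether onset is reported by arm, or what makes a visit the first. The Synopsis, under secondary endpoints, says positivity at the same cut-off will be assessed through week 32.

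The only power statement for secondary immune measures is in Section 9.1.2 (Secondary Immune Objectives): "The sample size with 27 patients in each arm is sufficient to detect a mean difference between the two study arms", "for an effect size (standardized unit) of at least 0.69 for normally distributed variables", with a directional 0.05 test and power of at least 0.80. It concerns differences between arms, not onset.

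**The concern.** The question is when a response first appears. ANOVA asks whether mean values are equal. An omnibus F test cannot name a visit. Visit contrasts can name only the first visit that reaches significance, which treats every earlier non-significant visit as no response yet. That visit depends on sample size and variance as well as on biology. A mean also mixes how many patients respond with how strongly they respond.

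Timing is the subject of the trial. Section 1.1 hypothesises that PAP-specific T cell responses depend on when ipilimumab is given, and T cell modulation by timing is a secondary objective. The two arms start ipilimumab about three weeks apart, and ELISPOT visits from week 4 to week 16 are also three weeks apart. If onset were reported by arm, an error of one visit in one arm would look the same as an effect of schedule.

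**Working it through.** **1. The plan's own figure.** Two-sample t, 27 per arm, effect 0.69, one-sided 0.05: noncentrality = 0.69 × √(27/2) = 2.535 on 52 df, giving power 0.804. The stated 0.80 reproduces. The plan gives no figure for the onset analysis.

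**2. Procedure examined.** This is an inference from the text: onset = first post-baseline visit with a significant increase over week 0.
- From the plan: 27 patients per arm, 8 visits, 7 comparisons, no adjustment.
- Assumed: two-sided 0.05, normal data, unit SD, equal correlation ρ between visits, and a step rise of d SD from week 7 that is then held.
- Error term: the repeated-measures residual, with (27−1)(8−1) = 182 df and critical value 1.973.
- Simulation: 20,000 series per scenario, repeated; repeat runs differ in the last digit.

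**3. No response at any visit.**
- Seven independent tests: 1 − 0.95^7 = 30.2%.
- Shared baseline and ρ 0.3 to 0.7: any significant contrast in about 23%. About half of these are falls from baseline, which no one would call a response.
- Significant increase: about 11-12%.
- Significant increase with a significant omnibus F required first: about 2%.

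**4. True rise from week 7, late or never named.** The noncentrality of one visit contrast is d / √(2(1−ρ)/27). For d = 0.5:
- ρ = 0.3: 0.5/0.2277 = 2.20. The chance of missing week 7 is about 1 − Φ(2.20 − 1.973) = 41%.
- ρ = 0.5: 0.5/0.1925 = 2.60, giving 27%.
- ρ = 0.7: 0.5/0.1491 = 3.35, giving 8%.

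Simulation agrees with this approximation. The simulated figures, counting increases only, are:

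| True rise | Late or never, ρ 0.3 to 0.7 | Two arms with identical onset are given different onsets |
|---|---|---|
| 0.5 SD | about 42% down to 8% | about 64% down to 20% |
| 0.69 SD | about 15% down to 0.4% | about 31% down to 6% |
| 1.0 SD | under 1% | about 5-6% |

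Too early (week 4) occurs in about 2.5% throughout. The last column applies only if onset is reported by arm. The 0.69 is a between-arm effect in the plan and is borrowed here for scale only.

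**5. Sensitivity.** A separate set of runs placed the true onset at week 13, with paired t tests and either equal correlation 0.5 or AR(1) correlation 0.7.
- Late or missed: 29-46% at 0.5 SD, 7-20% at 0.69 SD, under 2% at 1.0 SD.
- False early: about 6%.
- Dependence on sample size: with equal correlation 0.5 and a 0.3 SD rise, the correct visit is named in 28% of series with 27 patients and 52% with 54, although the true onset is identical.

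**6. Would adjustment repair it?** In the week-13 runs, Holm over the seven visits cuts the chance of any false significant visit to about 4%. At 0.5 SD, however, late or missed onset rises from 29-46% to 57-75%. Adjustment trades false onsets for late ones; it does not turn a test of means into an estimate of onset.

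**The case against.** The strongest reply is that the section says only ANOVA methods. Visit-by-visit testing, a first-significant-visit rule and reporting by arm are all inferred. The analyses are labelled exploratory and the absence of adjustment is declared. The cut-off is already to be assessed through week 32, and the ANOVA is an addition on the continuous scale. All of this stands, and it limits the weight of the point. It does not answer it: the exploratory label excuses weak error control, but not a method that targets a different quantity.

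Some stronger readings are tempting and the documents do not support them.
- A reader might conclude that the reported onset will usually be wrong. That holds only for small to moderate effects; at 1.0 SD the procedure is late in under 1%.
- A reader might quote a 23% false-onset rate. That counts significant falls and assumes no omnibus test first.
- A reader might apply the directional tests of Section 9.1.2, which would give a false upward onset in 17-21% of series. That section ties them to the effect of ipilimumab timing, a between-arm question.
- A reader might think that the cut-off gives onset directly. It does not: the section requires neither a negative baseline nor confirmation, and chance single-visit positives accumulate over seven visits.

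**Conclusion.** The point holds as a mismatch of method and question together with an unspecified rule. ANOVA on mean ELISPOT values does not estimate when a T cell response begins, and the section leaves open how a visit would be named first. The lack of adjustment is secondary. The size depends on assumed effect size and correlation and on the inferred procedure: lateness and chance differences between arms are material near 0.5 SD, smaller at 0.69 SD and slight at 1.0 SD.

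A reader might infer that the trial's conclusion on timing is compromised. It is not. The primary analysis is the week 20 IgG response proportion in each arm, tested by an exact binomial test, and neither it nor the sample size depends on this sentence. Severity is minor.

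**What to change.** State in Section 9.3.2.3 that no first-recognized visit will be named from ANOVA p-values, and replace the sentence with the following.
- For each arm and antigen, among patients negative at week 0, estimate the cumulative proportion with a first positive ELISPOT (≥ 10 spots/300,000) by visit, treating onset as interval-censored between visits. Give 95% confidence intervals and the between-arm difference. Report the number positive at week 0.
- Show beside it the proportion positive at each visit, and a sensitivity analysis requiring positivity at two consecutive visits, because isolated positives accumulate by chance.
- If the continuous scale is kept, show mean change from baseline at each visit with simultaneous 95% confidence intervals.

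The cost is SAP wording and a small amount of extra analysis from samples already planned. The main estimate makes less use of the continuous scale.
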